4.2. Exclusion Criteria

A subject will not be eligible for inclusion in this study if any of the following criteria apply:

CONCURRENT CONDITIONS/MEDICAL HISTORY (INCLUDES LIVER FUNCTION AND QTc INTERVAL)

1. ALT and bilirubin >1.5xULN (isolated bilirubin >1.5xULN is acceptable if bilirubin is fractionated and direct bilirubin <35%).
2. Current or chronic history of liver disease, or known hepatic or biliary abnormalities (with the exception of Gilbert's syndrome or asymptomatic gallstones)
3. QTcF > 450 msec (Section 4.3)
4. Current or chronic history of gastrointestinal illness or conditions interfering with normal gastrointestinal anatomy or motility. Examples include gastrointestinal bypass surgery, cholecystectomy, partial or total gastrectomy, small bowel resection, vagotomy, malabsorption, Crohn's disease, ulcerative colitis, IBS, or celiac sprue.
5. History of risk for or actual experience of complications from skin biopsy including excess bleeding, infection, or scarring/keloid formation (Part 2 only).

CONCOMITANT MEDICATIONS

6. Use of prescription or non-prescription drugs, including vitamins, herbal and dietary supplements (including St John's Wort) within 7 days (or 14 days if the drug is a potential enzyme inducer) or 5 half-lives (whichever is longer) prior to the first dose of study drug, unless in the opinion of the Investigator and GSK Medical Monitor the medication will not interfere with the study procedures or compromise subject safety. By exception, subject may take acetaminophen (≤ 2 grams/day) up to 48 hours prior to the first dose of study drug.

RELEVANT HABITS

7. Subjects should refrain from consumption of red wine, Seville oranges, grapefruit or grapefruit juice and/or pummelos, exotic citrus fruits, grapefruit hybrids or fruit juices from 7 days prior to the first dose of study medication until after the final dose.
8. History of regular alcohol consumption within 6 months of the study defined as an average weekly intake of >14 standard drinks. One standard drink is equivalent to 10 g of alcohol: 285 ml of beer, 100 ml of wine or 30 ml of 40% alcohol by volume distilled spirits.
9. For Part 1 and Part 2, urinary cotinine levels indicative of smoking or history or regular use of tobacco- or nicotine-containing products within 3 months prior to screening.

CONTRAINDICATIONS

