
recommended
 
If ALT ≥ 3xULN AND bilirubin < 2xULN and INR ≤ 1.5:
 
 Repeat liver chemistries (include ALT, AST, alkaline phosphatase, bilirubin) and perform liver event follow up assessments within 24-72 hrs Monitor subjects weekly until liver chemistries resolve, stabilize or return to within baseline 	
INR >1.5:
 
 Anti-nuclear antibody, anti-smooth muscle antibody, Type 1 anti-liver kidney microsomal antibodies, and quantitative total immunoglobulin G (IgG or gamma globulins). Serum acetaminophen adduct HPLC assay (quantifies potential acetaminophen contribution to liver injury in subjects with definite or likely acetaminophen use in the preceding week [James 2009]). Liver imaging (ultrasound, magnetic resonance, or computerised tomography) and /or liver biopsy to evaluate liver disease; complete Liver Imaging and/or Liver Biopsy CRF forms.

- Serum bilirubin fractionation should be performed if testing is available. If serum bilirubin fractionation is not immediately available, discontinue study treatment for that subject if ALT ≥ 3xULN **and** bilirubin ≥ 2xULN. Additionally, if serum bilirubin fractionation testing is unavailable, **record presence of detectable urinary bilirubin on dipstick**, indicating direct bilirubin elevations and suggesting liver injury.
- All events of ALT ≥ 3xULN **and** bilirubin ≥ 2xULN (>35% direct bilirubin) or ALT ≥ 3xULN **and** INR > 1.5, if INR measured, which may indicate severe liver injury (possible 'Hy's Law'), **must be reported as an SAE (excluding studies of hepatic impairment or cirrhosis)**; INR measurement is not required and the threshold value stated will not apply to subjects receiving anticoagulants
- Includes: Hepatitis A IgM antibody; Hepatitis B surface antigen and Hepatitis B Core Antibody (IgM); Hepatitis C RNA; Cytomegalovirus IgM antibody; Epstein-Barr viral capsid antigen IgM antibody (or if unavailable, obtain heterophile antibody or monospot testing); Hepatitis E IgM antibody

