**7.1.2.1. Clinical Laboratory**

Clinical laboratory results will be assessed for Part 1 and Part 2 separately. Laboratory evaluations will be summarized by the cohort of active treatments and pooling of placebo subjects within each part.

Clinical laboratory evaluations are divided into:

- **Haematology:** Platelet Count, RBC Count, WBC Count (absolute), Reticulocyte Count, Hemoglobin, Hematocrit, MCV, MCH, MCHC, Neutrophils, Lymphocytes, Monocytes, Eosinophils, Basophils;
- **Clinical Chemistry:** BUN, Creatinine, Glucose, Sodium, Bile Acids, Potassium, Chloride, bicarbonate, Calcium, AST (SGOT), ALT (SGPT), GGT, Alkaline phosphatase, Total and direct bilirubin, Uric Acid, Albumin, Total Protein;
- **Urinalysis:** Specific gravity, pH, glucose, protein, blood, ketones, Microscopic examination;
- **Liver Function Tests (LFTs):** total bilirubin, ALT.

Tables with descriptive statistics of change from baseline will be produced for all numerical tests for subjects with non-missing assessments. For categorical tests the number and percent of subjects for each category will be produced. Prior to analysis, all applicable numeric assessments will be converted to standard units.

Listing of all laboratory data for subjects with any value of PCI will be produced.

Listings of laboratory data with any value of PCI will be produced, too.

A listing will be created for subjects with any post baseline Liver Function Test (LFTs) with other Laboratory parameters, i.e. one of ALT and total bilirubin, classified as PCI..

Special figures, “matrix displays”, will be produced showing pairwise plots of the LFT values. To create these plots, the maximum value (over time) for each subject for each LFT will be calculated. Then for each pair of tests (e.g., total bilirubin vs ALT), each

subject will be plotted on the chart according to the maximum value of each. The subject markers (color and symbol) will be coded according to part /treatment.

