**11.5.2.2. Derivations and Handling of Missing Baseline Data**

Derivation	How Derived	Handling of Missing Data
Change from Baseline	= Post-Dose Visit Value – Baseline	Missing if either baseline or post is missing
%Change from Baseline	= (Post-Dose Visit Value – Baseline)/Baseline	Missing if either baseline or post is missing
Log Transformation	= [natural] log (PK Parameter)	Missing if PK parameter is missing
Back-Transformation	= EXP(estimate or confidence limit)	Missing if estimate or CL is missing
Maximum LFT	= maximum of that LFT (e.g., ALT) value for that subject over time	Missing only if all values of that LFT are missing for that subject
%AUC ex	= [AUC(0-inf) – AUC(0-t)] / AUC(0-inf) x 100	Missing if AUC(0-inf) is missing
Accumulation Ratio (R 0 )	= [AUC 0-τ on the final day (steady state)] / [AUC 0-τ on Day 1]	Missing if AUC 0-τ is missing for either Day 1 or final day
Accumulation Ratio (R s )	= [AUC 0-τ on the final day (steady state)] / [AUC 0-inf on Day 1]	Missing if either AUC 0-τ on final day or AUC(0-inf) on Day 1 is missing.
Corrected by adding the adjusting value to post dose TG values	
 
• Part 1 Day 1 Correction:                             
 
○ (Day -1 (1hr + 2hr)/2) – (Day 1 (1hr + 2hr)/2)
 
 
 
• Part 2:                             
 
○ Day 1 Correction:                                     
 
❖ (Day -1 (1hr + 2hr)/2) –
 
 
 
 
 
	Missing if any TG value is missing for either post dose or pre-dose at any time point

Derivation	How Derived	Handling of Missing Data
	
(Day 1 (1hr + 2hr)/2)
 
 
○ Day 14 Correction:                             
 
❖ (Day -1 (1hr + 2hr)/2) – (Day 14 (1hr + 2hr)/2)
 
 
 
	

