
 
Reporting for tables, figures and formal statistical analyses: 
 
Planned time relative to dosing will be used in figures, summaries, statistical analyses of concentration and lab data unless otherwise stated.
 
Actual time relative to dosing will be used to determine PK parameters, unless otherwise stated.
 
The impact of any major deviation from the planned assessment times and/or scheduled visit days on the analyses and interpretation of the results will be assessed as appropriate.
 
 
 
Reporting for Data Listings: 
 
Planned and actual time relative to study drug dosing will be shown in listings (Refer to IDSL Statistical Principle 5.05.1).
 
Unscheduled or unplanned readings will be presented within the subject's listings.
 
Visits outside the protocol defined time-windows (i.e. recorded as protocol deviations) will be included in listings but may be omitted from figures, summaries and statistical analyses if the deviation is great enough, according to Section 11.1.
 
 
 
	
Unscheduled Visits	

 
Unscheduled visits will not be included in summary tables or figures.
 
All unscheduled visits will be included in listings.
 
	
Descriptive Summary Statistics	
Continuous Data	Refer to IDSL Statistical Principle 6.06.1
Categorical Data	N, n, frequency, %
Reporting of Pharmacokinetic Concentration Data	
Descriptive Summary Statistics	Refer to IDSL Statistical Principle 6.06.1 Assign zero to NQ (BLQ) values (Refer to GUI_51487 for further details)
Reporting of Pharmacokinetic Parameters	
Descriptive Summary Statistics (Log Transformed)	N, n, geometric mean, 95% CI of geometric mean, standard deviation (SD) of logged data and [between and or within] geometric coefficient of variation (CV b/w (%)) will be reported, based on one-sample analysis: [1] $CV_b (\%) = \sqrt{\exp(SD^2) - 1} * 100$ (SD = SD of log transformed data) [2] $CV_w (\%) = \sqrt{\exp(MSE) - 1} * 100$ (MSE = mean square error from mixed effect model of loge-transformed data).
Parameters Not Log Transformed	Parameters t max , Ae, and CL r will not be transformed.
Summary Tables	All derived PK parameters which were listed in Table 7 in Section 8.1.3 above.

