## 11.12.5.3. Safety Figures

Safety: Figures					
No.	Population	IDSL / TST ID/ Example Shell	Title	Programming Notes (U)nique/(R)epeat	Deliverable
Laboratory					
3.1 3.2	Safety	LB8	Matrix Display of Maximum LFT (ALT, AST, ALP, and Total Bilirubin) Values	IDSL (U)	SAC
3.3 3.4	Safety	Non-Standard Mock SAFE_F1	Plot of Individual LFT (ALT, AST, ALP, and Total Bilirubin) Values vs. Study Time by Treatment Group and Test (Part X)	The name of X-axis is Days in Study. The name of Y-axis is the value of LFT (ALT, AST, ALP, and Total Bilirubin). One plot for each treatment group	SAC

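### The maximum-LFT figure has no post-dose limit and figures exclude unscheduled results, so a liver peak can be missing from the plots or a pre-dose value shown in its place

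*SAP*

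**What the plan says.** **The maximum.** SAP 7.1.2.1 describes pairwise plots of liver tests, with bilirubin against ALT as its example: "To create these plots, the maximum value (over time) for each subject for each LFT will be calculated". The derivation table in SAP 11.5.2.2 defines the variable as "maximum of that LFT (e.g., ALT) value for that subject over time", with the missing-data rule "Missing only if all values of that LFT are missing for that subject". SAP 11.12.5.3 lists the output as "Matrix Display of Maximum LFT (ALT, AST, ALP, and Total Bilirubin) Values" (Figures 3.1-3.2). Figures 3.3-3.4 plot individual liver values against days in study.

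**Unscheduled results.** SAP 11.5.3 states: "Unscheduled visits will not be included in summary tables or figures". The same block sends all unscheduled visits to the listings. For withdrawn subjects, SAP 11.7.1 puts the available planned data into tables and figures.

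**The protocol's liver rules.** After ALT ≥3×ULN, Appendix 2 (11.2) calls for repeat chemistries. If bilirubin and INR are not raised, sites must "perform liver event follow up assessments within 24-72 hrs" and then monitor weekly. If either is raised, the repeat is within 24 hours and monitoring is twice weekly.

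**Entry.** Exclusion criterion 1 (Protocol 4.2) allows a raised bilirubin before dosing: "isolated bilirubin >1.5xULN is acceptable if bilirubin is fractionated and direct bilirubin <35" per cent. Criterion 2 exempts Gilbert's syndrome.

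**The concern.** The bilirubin-against-ALT plot is there to show joint elevations on treatment. Two rules work against that purpose. Without a post-dose limit, screening and Day -1 values compete for the maximum. With unscheduled visits barred, the draws most likely to capture the top of a liver event are left out.

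The display can then fail in two directions. It can understate an event whose peak came at a repeat draw. It can also suggest a joint elevation by pairing a bilirubin taken before any drug with an ALT taken after it. Safety is the primary objective of both parts. Hepatic effects come first in the protocol's risk table (3.5.1), with dog ALT up to 2.71 times baseline in the 13-week study.

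**Working it through.** The plan states no figure to reproduce. The check sets the rules side by side and then applies them to one illustrative subject.

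**1. Is a post-dose limit implied?** Not in the text. In the same section (7.1.2.1), the sentence on the liver listing opens "A listing will be created for subjects with any post baseline Liver Function Test (LFTs", so the SAP writes the limit where it intends one. The missing-data rule in 11.5.2.2 would also plot a subject who had only pre-dose values.

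**2. Does the unscheduled-visit rule reach these displays?** Yes on its face. SAP Table 4 marks both liver displays as figures under the summary column, and 11.5.3 makes no exception.

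**3. Are Appendix 2 repeats unscheduled?** Mostly, apart from any that coincide with a planned visit. In Part 2, chemistry on Days 2-13 is planned on Days 2, 4 and 7 only (Protocol 6.1.3). The next planned draw is Day 14, so repeats after a Day 7 trigger fall in a gap. Repeats after a trigger at the follow-up visit fall after the last planned draw.

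**4. Can a pre-dose bilirubin be high enough to matter?** Yes. Criterion 1 can admit an isolated value above 1.5×ULN. SAP 11.8.1 flags bilirubin at ≥1.5×ULN, and also flags bilirubin at 1.5×ULN together with ALT ≥2×ULN.

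**5. Illustration.** All values are assumed, in multiples of ULN, on the Part 2 schedule. The subject stops treatment after the event and has no Day 14-17 draws.

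| Draw | ALT | Bilirubin |
|---|---|---|
| Screening | 1.4 | 2.1 |
| Day -1 | 1.0 | 1.6 |
| Day 1, 8h | 0.9 | 1.3 |
| Day 2 | 1.0 | 1.3 |
| Day 4 | 1.1 | 1.2 |
| Day 7 (case A / case B) | 1.3 / 3.1 | 1.2 / 1.3 |
| Day 10, unscheduled | 3.4 | 1.4 |
| Day 12, unscheduled | 4.2 | 1.5 |
| Follow-up | 1.2 | 1.2 |

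In case A the elevation is seen only at unscheduled draws. In case B it is first seen at the scheduled Day 7 draw. The plotted pair (ALT, bilirubin) is the maximum of each column over the values each rule admits:

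| Rule | Case A | Case B |
|---|---|---|
| SAP as written: all scheduled values, pre-dose included | 1.4, 2.1 | 3.1, 2.1 |
| 11.5.2.2 read alone: every value | 4.2, 2.1 | 4.2, 2.1 |
| Post-dose, scheduled and unscheduled | 4.2, 1.5 | 4.2, 1.5 |

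As written, ALT is understated by 4.2 − 1.4 = 2.8×ULN in case A and by 4.2 − 3.1 = 1.1×ULN in case B. It is not understated at all if the peak falls at a scheduled draw. In case B the plotted pair lies beyond ALT 3×ULN and bilirubin 2×ULN, the pair of levels that Appendix 2 uses. The largest bilirubin after dosing was 1.5×ULN. Reading 11.5.2.2 alone repairs the ALT value but still pairs it with the screening bilirubin.

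**The case against.** **The derivation rule may already admit unscheduled values.** Section 11.5.2.2 is specific to Maximum LFT, while 11.5.3 is a general reporting standard. Taking the derivation rule broadly enough to include screening but narrowly enough to exclude repeats is only one reading. This stands in part. The SAP does not say which rule governs, so two programmers could produce different figures. The broad reading also keeps the pre-dose problem and does nothing for Figures 3.3-3.4.

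**The standard shell may impose a limit.** Figures 3.1-3.2 use the sponsor's LB8 shell, which is not in the documents. It might restrict to post-baseline values; this cannot be confirmed or excluded.

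**A screening ALT shown as the maximum during an ALT event needs an unusual subject.** This stands. No scheduled post-dose ALT may exceed it. If the trigger falls at a scheduled draw, that value is plotted and only a later, higher one is lost. Bilirubin is more exposed, because entry permits a raised value.

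**A reader might infer that a liver event could vanish from the report.** The documents do not support that. Tables 3.21-3.22 summarise liver monitoring and stopping events and Listing 19 lists them. Listing 20 shows all laboratory data for any subject with a flagged value, and Listing 21 shows the flagged values. ALT ≥3×ULN with bilirubin ≥2×ULN (more than 35% direct) must be reported as an SAE, and SAEs are tabulated and listed.

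**A reader might extend the pre-dose criticism to Figures 3.3-3.4.** It does not apply there. Those plots have a time axis, so pre-dose points are identifiable and useful, and they help show when a matrix maximum was pre-dose.

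**Conclusion.** The point holds for the figures. As written, the matrix display can show a pre-dose value as the maximum or combine a pre-dose bilirubin with a post-dose ALT. All four liver figures can omit a peak seen only at unscheduled repeats. In the illustration the plotted ALT falls short by 0 to 2.8×ULN, depending on where the peak falls relative to the schedule.

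This rests on the SAP text alone: no post-dose limit hidden in the LB8 shell, and 11.5.3 taking precedence over 11.5.2.2. The subject's values are assumed. The documents reviewed report no liver stopping event, so whether any plotted point would change is unknown. It is tempting to size the problem by the share of planned draws that are pre-dose, but that would not measure missed or false joint elevations: with no drug effect most such maxima would be unremarkable.

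The displays are descriptive and no hypothesis is tested, so no inference is at risk. It is still worth correcting, because the figure's purpose is to show on-treatment joint elevations and the correction costs little.

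**What to change.** - In SAP 7.1.2.1 and 11.5.2.2, define Maximum LFT as the largest value after the first dose, from scheduled and unscheduled samples including follow-up, and missing only if no post-dose value exists.
- In SAP 11.5.3, exempt Figures 3.1-3.4 from the exclusion of unscheduled visits. Extend this to the planned-data rule for withdrawn subjects in 11.7.1.
- In the matrix display, show the baseline value separately, by symbol or panel. Keep the pre-dose points in Figures 3.3-3.4.

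Limit the exemption to these figures. SAP Table 4 plans no laboratory count of flagged values. Counts of this kind are planned for vital signs and ECG (7.1.3.1, 7.1.3.2), and a wider exemption would change those analyses without reason.

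The cost is a few sentences in the SAP and a filter in the figure programs. No new data are needed.

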### 7.1.3. Overview of Planned Other Safety Analyses

The safety analyses will be based on the Safety population, unless otherwise specified.

Table 5 provides an overview of the planned analyses, with further details of data displays being presented in Appendix 12: List of Data Displays.

**Table 5 Overview of Planned Other Safety Analyses**

Endpoint / Parameter/ Display Type	Absolute			Change from BL		
	Summary		Individual	Summary		Individual
	T	F	L	T	F	L
ECG						
ECG Findings	Y					
Change from Baseline in ECG Values by Visit				Y		
All ECG Data for Subjects with any Value of PCI			Y			
ECG Values of PCI			Y			
Abnormal ECG Findings			Y			
Vital Signs						
Change from Baseline in Vital Signs by Visit				Y		
Vital Signs Results by PCI Criteria	Y					
All Vital Signs for Subjects with any Value of PCI			Y			
Vital Signs of PCI			Y			
Other Exams						
Physical Exam			Y			

**NOTES:**

- T = Table, F = Figures, L = Listings, Y = Yes display generated, PCI = Potential Clinical Importance
- Summary = Represents TFL related to any summaries (i.e. descriptive statistics) of the observed raw data.
- Individual = Represents FL related to any displays of individual subject observed raw data.

#### 7.1.3.1. Vital Signs

Vital signs will be assessed for Part 1 and Part 2 separately. The assessment results will be summarized by the cohort of active treatments and pooling of placebo subjects within each part.

Tables with descriptive statistics of changes from baseline in vital signs (systolic blood pressure, diastolic blood pressure, pulse rate, heart rate, etc.) will be produced. Number and percent of subjects with any post baseline vital sign results of PCI will be produced.

A listing of vital signs data will be produced, including flagging for PCI.

**7.1.3.2. ECG**

Electrocardiograms (ECGs) will be assessed for Part 1 and Part 2 separately. The assessment results will be summarized by the cohort of active treatments and pooling of placebo subjects within each part.

Tables with descriptive statistics of changes from baseline will be produced for all numerical ECG tests of heart rate, PR interval, QRS interval, QT interval, QT with correction (Fridericia's formula), and number and percent of subjects will be produced for all categorical tests (ECG finding). Number and percent of subjects with any post baseline ECG results of PCI will be produced.

A listing of ECG data will be produced, including flagging for PCI.

**7.1.3.3. Other Exams**

Physical exam data will be listed, showing exam dates and any abnormalities found.

## 8. SECONDARY STATISTICAL ANALYSES

### 8.1. Pharmacokinetic Analyses

#### 8.1.1. Overview of Planned Pharmacokinetic Analyses

The pharmacokinetic (PK) analyses described below will be based on the PKC and PKP populations, unless otherwise specified. All summary tables and figures are for each part separately and all listings are for both parts combined into one, unless otherwise specified.

Table 6 below provides an overview of the planned analyses, with full details being presented in Appendix 12: Listing of Data Display.

**Table 6 Overview of Planned Pharmacokinetic Analyses**

Endpoint / Parameter/ Display Type	Untransformed							Log-Transformed						
	Stats Analysis			Summary		Individual		Stats Analysis			Summary		Individual	
	T	F	L	T	F	F	L	T	F	L	T	F	F	L
Concentration of GSK3008356														
PK Plasma Drug Concentration-time (Part 1 and Part 2 on Days 1 and 14)				Y	Y	Y	Y					Y	Y	
PK Trough Plasma Concentration-time (Part 2)				Y			Y							
PK Parameters														
Part 1: AUC 0-t , AUC 0-24 , AUC 0-∞ , C max				Y			Y*				Y			
Part 2: AUC 0-∞ , on Day 1, AUC (0-tau) , C max on Days 1 and 2. Accumulation Ratio (R 0 , R s and R cmax ),				Y			Y*				Y			
Parts 1 & 2: t max , t 1/2 , Ae, CLr				Y			Y*							
Part 1: Dose Proportionality (AUC 0-t , AUC 0-∞ , C max ) AUC 0-t , AUC 0-∞ , C max : Only applied for the single dosing. AUC 0-∞ : Applied for								Y		Y**				

Endpoint / Parameter/ Display Type	Untransformed						Log-Transformed							
	Stats Analysis			Summary		Individual		Stats Analysis			Summary		Individual	
	T	F	L	T	F	F	L	T	F	L	T	F	F	L
for all other cohorts with multiple dosing.														
Part 2: Dose Proportionality (AUC(0-∞) on Day 1, AUC (0-tau) , C max on Day 1 and Day 14								Y		Y**				
Part 2: Accumulation Ratio (R 0 , R cmax )								Y		Y**				
Part 2: Steady State (C trough )								Y		Y**				

**NOTES:**

- T = Table, F = Figure, L = Listings, Y = Display generated.
- Stats Analysis = Represents TFL related to any formal statistical analyses (i.e. modelling) conducted.
- Summary = Represents TFL related to any summaries (i.e. descriptive statistics) of the observed raw data.
- Individual = Represents FL related to any displays of individual subject observed raw data.
- \* Listing of All derived PK parameters will be produced in one listing by part.
- \*\* SAS Output of the Statistical Analyses from the statistical model.

